### **7.3.2 Premature termination or suspension of the study or a study site**

The study or a study site can be prematurely terminated or suspended by the sponsor. Reasons for termination of the study or a study site may include, but are not limited to, the following:

- Enrollment is unsatisfactory.
- The risks and benefits of continuing the study have been reassessed, and the risks outweigh any potential benefits.
- The incidence of AEs constitutes a potential health hazard to subjects.
- AESIs of severe intensity that represent respiratory function disorders or swallowing disorders, that are deemed to be related to IP administration, and are lasting >1 week will trigger premature termination of the study. The threshold for premature study termination is set to at least five subjects experiencing those AESIs for the 1st 50 subjects injected. Once 50 or more subjects have been treated in this study, the threshold is set to at least 10% of all treated subjects.
  - AESI terms related to respiratory function disorders are aspiration, diaphragmatic paralysis, dyspnoea, pneumonia aspiration, respiratory arrest, respiratory depression, and respiratory failure.

- AESI terms related to swallowing disorders are bulbar palsy, multiple cranial nerve palsies, dysphagia, hypoglossal nerve paresis, cranial nerve paresis, cranial nerve paralysis.
- New scientific data on the IP(s) do not justify a continuation of the study.
- Recommendation of the DMC.
- The investigator or study site exhibit serious and/or persistent non-adherence to the clinical study protocol, the Declaration of Helsinki, ICH–GCP, and/or applicable regulatory requirements.
- The sponsor decides to terminate the study or study site at any time for any other reason.

Furthermore, the study may be prematurely ended if the regulatory authority or the IEC/IRB has decided to terminate or suspend approval for the study, the study site, or the investigator.

If the study is prematurely terminated or suspended for any reason, the investigator must inform the subjects (if applicable) and the parent(s) and assure appropriate follow-up treatment. Within the timeframes noted in applicable regulations, the sponsor will promptly inform the investigators, study sites, the IEC/IRB, and regulatory authorities of the termination or suspension of the study, as well as provide reasons for the action.

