## 7.3 Removal of subjects from treatment or assessment

### 7.3.1 *Discontinuation of subjects*

In accordance with the Declaration of Helsinki and the IC form, the subject or parent(s) may discontinue the study at any time without any penalty or loss of benefits to which the subjects is otherwise entitled (see [Section 7.4.3](#)). Both the discontinuation of study and the reason(s) why the study was prematurely discontinued must be recorded in the subject's file and the eCRF. Date and discontinuation circumstances should be stated. Further details on discontinuation could be documented in the respective section of the "End of Study" form of the eCRF.

Subjects must be discontinued from the study by the investigator at any time for any of the following reasons:

- Withdrawal of IC.
- Treatment with any other IP in another clinical study.
- Treatment with any BoNT other than study medication.
- Pregnancy (no further administration of IP(s), blood draw, or any other interventional procedure will be performed; see [Section 10.4](#)).
- Any AE for which treatment continuation would constitute an unacceptably high risk for the subject.
- AESIs of severe intensity that represent respiratory function disorders or swallowing disorders will trigger the premature termination of a subject without re-exposition to IP. The terms for these severe AESIs are:
  - AESI terms related to respiratory function disorders are aspiration, diaphragmatic paralysis, dyspnoea, pneumonia aspiration, respiratory arrest, respiratory depression, and respiratory failure.
  - AESI terms related to swallowing disorders are bulbar palsy, multiple cranial nerve palsies, dysphagia, hypoglossal nerve paresis, cranial nerve paresis, cranial nerve paralysis.
- Injection treatment cannot be performed for any reason, not even with local anesthesia and/or analgosedation.
- Eligibility criteria are not met after the previous injection of IP in the respective treatment cycle (MP or OLEX) (see [Section 7.3.1](#)).

The DMC may recommend further criteria for discontinuation. Deviations from this study protocol, or conditions comprising exclusion criteria established in [Section 7.3](#) that arise after the subject has been included in the study may (but will not necessarily) lead to the discontinuation of subject's study participation. All such conditions must be properly documented.

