### **10.1.3 Categories of actions taken and outcome**

Action(s) taken with IP:

- Drug withdrawn.
- Dose reduced.
- Dose increased.
- Dose not changed.
- Unknown.
- Not applicable.
- Drug withdrawn temporarily

The reportable outcomes and/or sequelae of an AE are as follows:

- Recovered/resolved.
- Recovering/resolving.
- Not recovered/not resolved.
- Recovered/resolved with sequelae.
- Fatal.
- Unknown.

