### **10.2 Definition of a serious adverse event**

An SAE is any untoward medical occurrence, at any dose, that:

- Results in death.
- Is life-threatening.
- Requires inpatient hospitalization, or prolongation of existing hospitalization.

---

 If there is more than 1 AE, only the AE leading to death will be attributed with a 'fatal' outcome.

 The term 'life-threatening' in the definition of 'serious' refers to an event in which the child/adolescent was at risk of death at the time of the event; it does not refer to an event that hypothetically might have caused death if it were more severe.

- Results in persistent or significant disability/incapacity.
- Is a congenital anomaly/birth defect.
- Consists of any other medically important condition.

In case of death, an autopsy report should be submitted (if available). The date and cause of death should be recorded.

Hospitalizations for elective treatments planned before screening and which are documented in the subject's source data are usually not regarded as SAEs. Hospitalizations for analgo-sedation starting one day before or on the day of injection treatment (V2 and V7) for organizational reasons only (e.g. to allow for an early start of the Injection Visits in the morning in subjects living far from the site) are generally not regarded as SAEs. However, if any event during or after analgo-sedation would trigger an overnight stay, this will qualify as SAE. The same applies, if analgo-sedation was started in an outpatient setting at the site and then has been changed to an inpatient setting, e.g. due to an unexpectedly long monitoring phase post intervention.

All SAEs that occur during the study period, whether considered to be related to IP or not, must be reported by telefax, telephone or e-mail within 24 hours of knowledge of the event. SAE report forms are provided in the ISF.

Although all information required for completion of an SAE report form may not be available within the specified time period, an initial report should be submitted if the following minimal information is available:

- An identifiable subject (number, initials).
- A suspect product.
- An identifiable reporting source (investigator/study site identification).
- An event or outcome that can be identified as serious.

The report must be delivered to the individual(s) listed below.

[REDACTED]

[REDACTED]

---

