 - start date/time completely missing and end date/time not before date/time of first exposure in the MP, set start date/time to date/time of first exposure in the MP
 - if AE end date and time are missing set end date to study end date (i.e. last contact or last visit of the study) and end time to 23:59
 - if AE end date/time is partially missing, set end day to last day of the given month or end day/month to 31/12 of the given end year and missing end time to 23:59
 - if AE end time is missing set time to 23:59.

Imputation rules for multiple records in case of AE worsening:

- For missing AE start date/time the imputation strategies as defined above will be applied to all records of the same AE.
- For missing TEAE end date/time the imputation strategies as defined above will be applied to the last record of the same TEAE.

Calculation of time to onset/duration of AEs [days]:

- Time to onset of an AE is defined as start date of AE - date of most recent administration of study drug [+ 1 for AE starting after start of treatment]
- The duration will be calculated as stop date - onset date + 1 for each episode of worsening.

Incidences will be calculated for TEAEs overall (MP+OLEX), overall OLEX and by injection cycle on the system organ class (SOC) level and on the preferred term (PT) level (i.e., total, by worst intensity, by worst relationship, and by worst outcome). Listings and, if applicable, tables displaying incidences for TEAEs leading to discontinuation, serious TEAEs, related serious TEAEs, TEAEs of special interest, and deaths will also be provided. Additionally the number and percentage of subjects with at least one non-serious TEAE with incidence $\geq 5\%$

in any MP treatment group or in the OLEX Period and number of non-serious TEAE will be displayed by SOC level and PT level. Time to onset and duration of AEs will be listed. Time to onset and duration of AEs will be listed.

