For any missing data of adverse events, a worst case strategy will be applied for all analysis tables. The intensity will be imputed by the worst intensity “severe”, the causal relationship will be imputed by the worst relationship “drug related”. Missing data of the worst outcome will be imputed by “unknown”. If a subject has more than one outcome within a preferred term (PT) only the worst outcome will be used in the frequency tables. Also on subject level only the worst outcome category per subject will be counted in the frequency table. The worst outcome is defined in the following order:

- recovered/resolved
- recovered/resolved with sequelae
- recovering/resolving
- not recovered/not resolved
- unknown
- fatal

TEAESIs are defined as TEAEs that are thought to possibly indicate toxin spread. A list of adverse events of special interest possibly indicating toxin spread is given in **Table 1: List of Adverse Events of Special Interest Possibly Indicating Toxin Spread.**

Table 1: List of Adverse Events of Special Interest Possibly Indicating Toxin Spread

MedDRA PT	MedDRA PT
Accommodation disorder	IIIrd nerve paresis
Areflexia	Ileus paralytic
Aspiration	IVth nerve paresis
Botulism	Monoparesis
Bradycardia	Muscular weakness
Bulbar palsy	Paralysis
Constipation	Paraparesis
Cranial nerve palsies multiple	Paresis
Cranial nerve paralysis	Paresis cranial nerve
Diaphragmatic paralysis	Peripheral nerve palsy
Diplopia	Peripheral paralysis
Dry mouth	Pelvic floor muscle weakness
Dysarthria	Pneumonia aspiration
Dysphagia	Pupillary reflex impaired
Dysphonia	Quadriparesis
Dyspnoea	Respiratory arrest
Extraocular muscle paresis	Respiratory depression
Eyelid function disorder	Respiratory failure
Eyelid ptosis	Speech disorder
Facial paralysis	Trigeminal nerve paresis
Facial paresis	Urinary retention
Hemiparesis	Vision blurred
Hypoglossal nerve paresis	Vocal cord paralysis
Hyporeflexia	Vocal cord paresis
Hypotonia	
Wording of PTs is according to MedDRA version 21.0	

To fulfill FDA requirements, TEAE data will be screened for suicidal events. The MedDRA PTs of all TEAEs will be checked using standard MedDRA query (SMQ) „Suicide/self-injury“. Resulting TEAE findings will be listed in a separate listing. A list of the MedDRA PTs of the SMQ „Suicide/self-injury is given in Table 2.

Table 2: List of Adverse Events of Standard MedDRA Query „Suicide/self-injury“

MedDRA PT:	MedDRA PT:
Columbia suicide severity rating scale abnormal	Self injurious behaviour

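### The only numeric study-termination trigger counts a severe, related respiratory or swallowing event only if it lasts more than a week; read literally, one that kills sooner is left out

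*Protocol*

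**What the plan says.** Section 7.3.2 of the Protocol (numbered 7.4.2 in its table of contents) lists reasons for ending the study. The list is expressly open-ended. Most entries are matters of judgment: poor enrolment, a changed risk-benefit view, an AE incidence that is a hazard to subjects, new data, a DMC recommendation, or any other sponsor decision. One entry is automatic and numeric. It concerns severe AESIs from a named list of respiratory and swallowing terms "that are deemed to be related to IP administration, and are lasting >1 week will trigger premature termination of the study". At least five subjects with such events among the first 50 injected meet the threshold; from 50 treated subjects onward "the threshold is set to at least 10% of all treated subjects".

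The subject-level rule in Section 7.3.1 uses the same term lists. There, a severe listed event "will trigger the premature termination of a subject without re-exposition to IP", with no condition on duration.

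Death is a recorded outcome. Section 10.1.3 introduces its list with "The reportable outcomes and/or sequelae of an AE are as follows", and fatal is one of the entries.

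**The concern.** A minimum duration is a sensible way to keep brief, recovered episodes out of a count that can end a study. An event cut short by death is brief for the opposite reason, yet the wording treats the two alike. The term list includes respiratory arrest, respiratory failure and diaphragmatic paralysis, any of which could kill within a week. Section 4.3 says there is no monitored experience with this preparation in children or adolescents, and Section 8.2.6 names respiratory-muscle paralysis among the signs of overdose. These are the events the trigger was written for.

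At stake is whether the one rule that does not depend on judgment counts the gravest form of the event it monitors.

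**Working it through.** **Thresholds as stated.** 5/50 = 10%, so the two parts of the rule agree at 50 subjects. Later, 10% of 100 is 10, 10% of 200 is 20, and 10% of 344 is 34.4, so 35 subjects (assuming the planned 344 are all treated).

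**Conditions for one event to count.** All must hold:
- a listed respiratory or swallowing term;
- severe intensity;
- deemed related to the investigational product (IP);
- lasting more than one week.

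The threshold sentence then refers back to events meeting these conditions. Neither Section 7.3.2 nor the supplied DMC text (Protocol 2.3, 10.2, 10.3 and 12.4.7.3; SAP 7.7.3) makes an exception for death.

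**Two events compared.**
- Severe related dysphagia lasting 8 days: all four conditions hold; adds 1.
- Severe related respiratory failure, fatal on day 3: the duration condition fails on a literal reading; adds 0.

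**How long did the fatal event last?** Section 7.3.2 does not say. SAP Section 7.5.2 has rules written for AE tables and listings, not for this trigger, so they serve only as a cross-check:
- "The duration will be calculated as stop date - onset date + 1 for each episode of worsening". With onset on day 1 and death on day 3 as the stop date, 3 - 1 + 1 = 3 days, which is not more than 7.
- If the event is left without a stop date, "if AE end date and time are missing set end date to study end date", meaning last contact or last visit. That is also about day 3, again giving 3 days.

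Elapsed time gives 3 - 1 = 2 days. All three readings leave the event out.

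**Effect on the decision.** Suppose four of the first 50 subjects have qualifying events and a fifth has a related respiratory failure fatal on day 3.
- As written: 4/50 = 8%, below five subjects; no trigger.
- With the death counted: 5/50 = 10%; trigger met.

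The same one-subject difference applies at full enrolment: 34/344 = 9.9% does not meet 10%, and 35/344 = 10.2% does.

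The documents give no expected rate for such events, so no probability of a changed decision can be stated.

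**The case against.** The strongest reply is that deaths are handled elsewhere. A death is an SAE, reportable within 24 hours, and the DMC reviews all SAEs and AESIs and may unblind individual subjects. The DMC can recommend stopping, the sponsor can stop for any reason, and a regulator or ethics committee can withdraw approval. The numeric rule may therefore be a backstop for accumulating persistent events, with deaths judged one by one. A separate rule may also sit in Appendix 16.2 or the DMC charter, neither of which was supplied. All of this stands and keeps the point minor. It does not explain why a count intended to run without judgment should omit the worst case. The protocol gives no such rationale.

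It can also be argued that an event unresolved at death is a lasting one. That reading is possible, but the text does not state it, and an automatic trigger should not depend on it.

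A reader might infer more than the documents support:
- *That the trigger contradicts the SAP's own ranking of outcomes.* The list introduced by "The worst outcome is defined in the following order" does end with fatal, but it only selects which outcome to tabulate when a subject has several. It places unknown above not recovered and has no role in stopping.
- *That there is an exact cut-off between death on day 7 and day 8.* That depends on the SAP's added day. For death 7 days after onset, the SAP formula gives 8 days and elapsed time gives 7, and the protocol adopts neither for this rule.
- *That Section 7.3.1 shows an inconsistency.* It governs re-exposure of one subject and has no relatedness condition either. A stricter test for ending the study is legitimate.

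**Conclusion.** The point holds as a gap in wording. Read literally, the only numeric trigger leaves out a severe, related, listed event that ends in death within a week; on the most generous reading the clause is unclear. The size is one subject per such event in the automatic count. That decides the outcome only when the count is otherwise one short, as in 4 versus 5 of the first 50.

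It would be wrong to infer that an early related death could not stop the study: every discretionary route remains open. The conclusion rests on the supplied text alone and would need revisiting if Appendix 16.2 or the DMC charter contains a fatal-event rule. Severity is minor; this is a cheap improvement.

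**What to change.** In Section 7.3.2, reword the duration condition to *and are lasting >1 week, or are fatal or unresolved at the subject's death*. The alternative replaces only the duration test; the severity, relatedness, term-list and threshold conditions stay. Align Appendix 16.2 and the DMC charter if they repeat the rule.

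Both halves of the addition are needed. Under the footnote to Section 10.1.3, when there are several AEs, "only the AE leading to death will be attributed with a" fatal outcome. A listed event still present when another AE caused the death would be missed if the wording covered fatal events alone.

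Short, non-fatal events should stay out. Under Section 10.1.2 an event is related if a relationship cannot be ruled out, so brief respiratory depression from sedation could otherwise enter the count.

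No new data are needed: AE outcome, stop date and date of death are already collected. The change is not purely administrative, so Section 3.1 requires ethics approval, with approximately 45 sites planned; it is best added to the next amendment. The downside is that the trigger may be reached slightly sooner, and a fatal sedation-related event for which the IP cannot be ruled out would count.

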### **7.3.3 Provision of care for subjects after study discontinuation**

After study discontinuation, the subjects will be treated by their physician according to their medical condition and standard treatments in the country concerned. For further information, see [Section 3.3.4](#).

Subjects who discontinue prematurely may receive treatment at the discretion of the investigator (e.g., referral to orthopedic surgery, switch to another BoNT, oral/intrathecal antispastic medication, and local alcohol or phenol injections). The investigator and/or the subject's physician are free to apply any approved antispastic treatment, physiotherapy, orthotic management, and any other rehabilitation treatment to treat spasticity.

## 8 TREATMENTS

### 8.1 Investigational product(s)

#### 8.1.1 Description of investigational product(s)

In the double-blind MP, subjects will be randomly allocated to receive active treatment in one of three parallel dose groups (high, mid, and low).

In the open-label OLEX, all subjects will receive active treatment in the same dose group.

Active treatment:	NT 201, 100 units, powder for solution for injection
International non-proprietary name of active ingredient:	An international non-proprietary name for the drug substance has not been assigned. The assigned USAN for the active ingredient is incobotulinumtoxinA.
Excipients:	Sucrose, human serum albumin.

The IP will be supplied in a clear glass vial. Each vial of NT 201 contains an amount of sterile lyophilized solid material with biological activity of 100 mouse LD50U (calculated median lethal intraperitoneal dose), which corresponds to approximately 600 pg of neurotoxin. The excipients of the final formulation of NT 101 (that is the active neurotoxin molecule in the preparation of NT 201) are sucrose for stabilization and human serum albumin to prevent adsorption of the neurotoxin on container, syringe, and needle. NT 201 contains no hemagglutinins.

In MP only, PBO will be used for preparation of the injection solution for the mid and low dose group. PBO vials with lyophilisate have identical appearance and solution properties to NT 201 vials. The PBO vials contain human serum albumin and sucrose but do not contain NT 101.

PBO for IP preparation for mid and low dose group:	PBO vial containing excipients of NT 201, powder for solution for injection
Excipients:	Sucrose, human serum albumin.

The IP might be supplied in more than one shipment at different time points of the study.

##### 8.1.1.1 Instructions for preparation

[Redacted]

[Redacted]

[Redacted]

[Redacted]

[Redacted]	[Redacted]	[Redacted]	[Redacted]
[Redacted]	[Redacted]	[Redacted]	[Redacted]
[Redacted]	[Redacted]	[Redacted]	[Redacted]
[Redacted]	[Redacted]	[Redacted]	[Redacted]
[Redacted]			

[Redacted]

[Redacted]

[Redacted]

[REDACTED]

[REDACTED]

[REDACTED]

[REDACTED]

[REDACTED]

#### 8.1.1.2 *Instructions for administration*

##### **Process for determination of injection scheme**

In this study five pre-defined treatment combinations (A-E, see below) of UL alone or combined UL and LL injections will be allowed. The investigator first has to judge based on his clinical experience in the indication spasticity due to CP, if treatment in one of the five combinations is appropriate for the clinical condition of a subject. This judgment will be based on the dose administered in the high dose group of this trial since (a) actual randomization to dose groups in MP will be blinded and (b) all subjects will receive

doses of MP's high dose group in OLEX. Since the actual dose of IP in MP will be blinded, injection volume per muscle and per pattern will be controlled and documented in the eCRF. Conversion of NT 201 doses to volumes will be facilitated by a conversion table (see [Appendix 16.5](#)).

Dose calculations for injection treatment in an individual subject should also consider the GMFCS levels I-III or IV-V, the total dose per kg BW, the maximum dose allowed in this study, the selection of clinical patterns for treatment, the dose per muscle, and the dose per injection site.

To be eligible for injection with IP each clinical target pattern in UL(s) and LL(s) must show an AS score of  $\geq 2$  at the Baseline Injection Visit V2.

In OLEX, eligibility for reinjection among other criteria is given at an AS  $\geq 2$  in the respective clinical pattern. At AS=1 the decision for injection is up to the investigator. At AS=0 no injection is allowed. For eligibility criteria for reinjection in OLEX see also [Section 7.3.1](#).

The investigator will distribute the fixed dose per UL between selected muscles within pre-defined dose ranges and number of injection sites per muscle (see [Table 14](#) and [Table 15](#)). The main clinical target patterns for UL treatment chosen at V2 must be kept throughout study participation and must be injected with a fixed total dose (see [Table 14](#)). For subjects with bilateral UL treatment the main clinical target patterns of both sides must be kept. Adaptations for the main clinical target patterns are only allowed within the dose ranges per muscle and number per injection sites given in [Table 14](#) as long as the total fixed dose per main clinical target pattern is kept.

Depending on which body side(s) and limb(s) are affected by UL spasticity, uni- or bilateral UL will be administered in five treatment combinations (A-E) at Baseline Injection Visit V2 (see for details see [Table 6](#) to [Table 13](#)). It will not be allowed to change the treatment combination chosen at V2 or to change the body side of treatment in unilaterally treated subjects.

In subjects with additional treatment of LL(s) in treatment combinations B. – E. it will be allowed to change the LL patterns chosen at V2 in further treatment cycles. Regulations for doses per muscle, number of injection sites of [Table 15](#) and for total dose to the LL(s) must be respected.

It is recommended to consider pre-existing medical co-morbidities, muscle size and activity, and experience from previous BoNT treatments of the subject (if applicable). No more than 20 U/kg BW NT 201 (max. total body dose of 500 U for subjects  $\geq 25$  kg BW) will be injected in this study. For safety reasons, the upper dose limit for subjects with GMFCS levels IV-V is restricted to 16 U/kg BW NT 201 (max. total body dose of 400 U for subjects  $\geq 25$  kg BW).

Doses for subjects of <25 kg BW are displayed in tables [Appendix 16.4](#). Above 25 kg BW fixed doses will be injected. The distribution of the total dose to clinical patterns per limb in this study is as follows:

[figure not shown]
[figure not shown]
